4.2 Study Design

PQ-421a-003 is a double-masked, randomized, controlled, multiple-dose study to evaluate the efficacy, safety, and tolerability of ultevursen in subjects with RP due to mutations in exon 13 of the *USH2A* gene.

At study start subjects will be randomized to one of the following treatment groups:

- Group 1: Ultевурсен 180/60 µg (180 µg loading dose administered on Day 1, 60 µg maintenance dose administered at Month 3 and every 6 months thereafter; n = 27)
- Group 2: Ultевурсен 60/60 µg (60 µg loading dose administered on Day 1, 60 µg maintenance dose administered at Month 3 and every 6 months thereafter; n = 27)
- Group 3: Sham-procedure (administered on Day 1, Month 3 and every 6 months thereafter; n = 27)

The primary endpoint will be assessed at 18 months of treatment. Analysis of all other efficacy and safety parameters will also be reported at that time point. All efficacy and safety parameters will continue to be followed until Month 24.

The same safety monitoring protocol and efficacy assessments will apply to both eyes.

Dosing will be only in the TE (i.e., study eye). The CE will not be dosed.

Changes to the above-described treatment plan may be warranted and will be guided by the ongoing assessment of benefit-risk, with concurrence from the Medical Monitor.

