9.4.1 Adverse Event Reporting Period

After signing of the Informed Consent all significant medical conditions including signs/symptoms of the underlying disease and known pre-existing medical conditions found during the screening period and up to initiation of dosing will be captured as medical history. Any event/condition, including those related to participation in the study or study procedures, those not related to underlying disease or pre-existing medical conditions already part of medical

history, and occurring before first dose of study treatment will be captured as a non-treatment emergent AE.

Any event/condition noted once the subject receives their dose of study drug will be captured as a treatment emergent AE. All AEs and SAEs regardless of attribution will be collected until at least 90 days following the last administration of study drug or the subject's EOS visit, whichever is later. At the last scheduled visit, the Investigator should instruct each subject to report to the Investigator any subsequent AEs/SAEs that the subject's personal physician believes could be related to prior study treatment.

SAEs unrelated to study treatment and non-serious AEs are to be followed until the last scheduled study visit (EOS visit), with the outcome at that point of time to be recorded in the eCRF. SAEs related to study treatment (Serious Adverse Drug Reactions) are to be followed until resolution or until they return to baseline, stabilize, or the subject is lost to follow-up. Resolution of AEs and SAEs (with dates) should be documented on the AE eCRF and SAE form (if applicable) and in the subject's medical record to facilitate source data verification. For some SAEs, the Sponsor or its designee may follow up by telephone, facsimile, electronic mail, and/or a monitoring visit to obtain additional case details deemed necessary to appropriately evaluate the SAE report (e.g., hospital discharge summary, consultant report, or autopsy report).

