### **2.2. Study Termination**

In this context, the Analysis Description (AD) is abbreviated and describes the populations for analysis, data handling rules, statistical methods, and formats for data presentation that will be required for the close out of the study, after all randomized subjects have completed the end of study visit and the database is locked.

The summary tabulations and listings that will be produced for the close out of the study, will provide the basis for the appropriate sections of the abbreviated clinical study report (CSR) or equivalent document.

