## **5.6. Safety – Adverse events**

A treatment-emergent AE (TEAE) is defined as an event that was not present prior to administration of the dose of study drug (ultevursen or sham-procedure) and present after the dose or if it represents the exacerbation of an event that was present prior to the dose.

Adverse events will be summarized by treatment group separately as follows:

- For non-ocular AE:
  - by subject, therefore, in any tabulation, a subject contributes only once to the count for a given adverse event (System Organ Class [SOC] or Preferred Term [PT])
  - and during the overall study period (i.e., up to the last visit for the last subject).

- Time to onset will be calculated in hours, relative to the last dose received, irrespective of which eye received the last dose (i.e., TE or CE).
- For ocular AE:
  - by eye frequencies, separately for the TE and the CE, therefore, in any tabulation, an eye contributes only once to the count for a given AE (by SOC or PT). AEs that are reported in both eyes (i.e., OU) will be reported individually by eye in the tabular summaries.
  - and during the overall study period (i.e., up to the last visit for the last subject).
  - Time to onset will be calculated in hours, relative to the last dose received in the eye experiencing the ocular AE.

Unless otherwise stated, any summary of any type of TEAEs which includes the SOC and PT of the events will order the SOC and the PTs within the SOC by descending incidence of PT.

The following summary tables will be produced separately according to the type of AEs (ocular/non-ocular where applicable) as defined above:

- Overview of Ocular Adverse Events for Treatment Eye during the overall study period (Safety Population)
- Overview of Ocular Adverse Events for Contralateral Eye during the overall study period (Safety Population)
- Overview of Non-Ocular Adverse Events during the overall study period (Safety Population)
- Summary of Ocular Treatment-Emergent Adverse Events for Treatment Eye during the overall study period by MedDRA System Organ Class and Preferred Term (Safety Population)
- Summary of Ocular Treatment-Emergent Adverse Events for Contralateral Eye during the overall study period by MedDRA System Organ Class and Preferred Term (Safety Population).
- SAEs
- AESIs

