## **6. CHANGES TO PLANNED ANALYSES**

As the study is prematurely stopped by Sponsor's decision, no formal statistical analysis will be produced. Only disposition, demographic and baseline characteristics, and overview of AEs will be summarized in tables. By-subjects data listings will be produced based on raw data.

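### After the early stop, the SAP's adverse event tables can close before the protocol's 90-day post-dose collection period has ended for recently dosed subjects

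*SAP*

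**What the plan says.** - **Protocol 9.4.1** has all adverse events and SAEs, whatever their attribution, "collected until at least 90 days following the last administration of study drug or the subject's EOS visit, whichever is later". The same section has a separate rule on following events already reported: unrelated SAEs and non-serious events "are to be followed until the last scheduled study visit (EOS visit").
- **Protocol 4.2** schedules the sham procedure as "administered on Day 1, Month 3 and every 6 months thereafter", with the same timing in the two active arms. Follow-up is planned to Month 24.
- **Protocol 13.6** defines the end of the study as the last visit of the last subject globally.
- **SAP 5.6** summarises adverse events "during the overall study period (i.e., up to the last visit for the last subject"). The same limit is given for non-ocular and for ocular events.
- **SAP 2.2** sets the close-out analysis "after all randomized subjects have completed the end of study visit and the database is locked".
- **SAP 6** states: "As the study is prematurely stopped by Sponsor's decision, no formal statistical analysis will be produced". It leaves tables only for disposition, baseline characteristics and adverse events, plus by-subject listings. Its visible text does not record any change to the 90-day period, and the visible SAP does not mention that period elsewhere.

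**The concern.** The protocol's limit has two limbs: the EOS visit, and 90 days after the last administration. The SAP carries over only a visit-based limit. That is harmless while the last dose and EOS are about 90 days apart. This SAP, however, is written for a study that was stopped, and the EOS visit of a subject still in follow-up can then fall at any distance from the last dose.

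At stake is the completeness of the only outcome tables that remain. For the most recently dosed subjects, late post-dose events could be ones the protocol requires to be collected but the tables leave out. Leaving out such events can only lower the counts. How much post-dose time is left out depends on where a subject stood in the dosing cycle, and no planned table shows it.

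**Working it through.** No power or alpha calculation applies. The check compares two time windows.

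**Notation.** For subject i, let L be the date of the last administration and E the EOS date. Let V be the last subject's last visit, so V is on or after every E.

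- Protocol 9.4.1 window ends at max(L + 90 days, E).
- SAP 5.6 tables end at V.
- Days required by the protocol but outside the tables: U = max(0, 90 − (V − L)). The E limb drops out because E is never later than V.

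**1. Planned schedule.** Doses fall at Months 0, 3, 9, 15 and 21. With a month of 30.44 days, Month 21 to Month 24 is 3 × 30.44 = 91.3 days. So U = max(0, 90 − 91.3) = 0. If a month meant four weeks, the gap would be 3 × 28 = 84 days and U = 6. The windows therefore nearly coincide in a study that runs to plan.

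**2. After the stop.** The interval V − L is not given, so it is varied:

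| V − L (days) | U (days) |
|---|---|
| 30 | 90 − 30 = 60 |
| 61 | 90 − 61 = 29 |
| 90 or more | 0 |

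**3. How many subjects could be exposed.** Assume that dosing continued up to the stop, that subjects were spread evenly over a 6-month cycle (about 183 days), and that every EOS came g days after the stop. The share whose own EOS precedes day 90 is max(0, 90 − g)/183:

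| g (days) | Share |
|---|---|
| 0 | 90/183 = 49% |
| 30 | 60/183 = 33% |
| 60 | 30/183 = 16% |
| 90 or more | 0% |

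With EOS at the stop, the share for subjects between Day 1 and Month 3 is 90/91.3 = 99%. Over the whole schedule it is (5 × 90)/730.5 = 62%.

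These shares use E, whereas the SAP cuts at V. Since V is never earlier than E, they are upper bounds on the subjects exposed to the SAP cut. They would be reached only if all EOS visits fell on one day. An exposed subject loses an event from the tables only if one starts in the uncovered days.

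**4. A sign in the imputation rules.** SAP 5.6.1 caps partial event end dates at the subject's own last visit. An event starting after that visit with a partial end date would be given an end before its start. Imputation serves only to classify events as treatment-emergent, so this need not change a count. It does suggest that events after the last visit were not considered.

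**The case against.** Several objections have force.

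- **The cut is study-wide.** A reader might infer that each subject's events are cut at that subject's own EOS visit. SAP 5.6 does not say so. A subject who finishes early still has every collected event tabulated up to the last subject's last visit. This stands and narrows the point to subjects dosed less than 90 days before that date.
- **The limit matches Protocol 13.6.** This also stands: the SAP's limit is the protocol's own end-of-study date, so part of the tension lies between Protocol 9.4.1 and 13.6. But 9.4.1 is the specific rule on event collection, and its later-of wording provides for collection after EOS. Its rule about following events until EOS concerns events already reported and does not shorten collection.
- **The SAP does not govern collection or fix a lock date.** Correct. SAP 2.2 names completed EOS visits and lock as two conditions and does not say that lock follows at once. It also does not say that lock waits for the 90 days.
- **The listings have no stated cut-off.** Also correct: SAP 5.7 and SAP 6 set none. An event collected before lock would be listed even if no table counted it. The listings still cannot show what was not collected by lock.
- **The deciding dates may be in text that is not public.** The body of Protocol 7.4, the schedule of events and the opening of SAP 2.2 are not visible. Their absence is no fault of the plan, and it means that actual loss cannot be shown.

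**Conclusion.** The inconsistency is real and limited. As worded, SAP 5.6 can exclude from the tables events that Protocol 9.4.1 requires to be collected, and the visible SAP does not record this as a departure. It concerns only subjects dosed less than 90 days before the last subject's last visit, and only events starting after that visit and within 90 days of dosing. The uncovered time is at most 90 days per subject. It is zero for everyone if that visit came at least 90 days after every subject's last dose.

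Two stronger readings are not supported. The 49%, 33% and 16% shares might be taken as the fraction of subjects or events lost. They are upper bounds on exposed subjects under assumed EOS timing and an even spread over the cycle. A reader might also infer a bias between arms. All three arms share one schedule and were randomised, and nothing in the documents shows a difference. No inferential result is affected, since none is planned. The correction is still worthwhile because these are the only outcome tables left and the change is small.

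**What to change.** 1. **SAP 5.6:** state that the adverse event tables include all events collected under Protocol 9.4.1, that is, up to the last subject's last visit or 90 days after each subject's last administration, whichever is later. Add that no later reported event is removed. A purely per-subject cut-off should not replace the study-wide one: it could drop late events that are now counted, including possibly related SAEs after participation, which Protocol 9.5 requires to be reported.
2. **SAP 2.2:** state that database lock follows completion of the 9.4.1 collection period for every treated subject. If that is not intended, record the departure and its reason in SAP 6.
3. **Protocol 9.4.1 and 13.6:** reconcile the collection period with the end-of-study definition.
4. **Optional:** list days from last administration to end of event collection, so that readers can see each subject's post-dose follow-up.

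The cost is a few sentences. Lock could move by up to about 90 days if some subjects were dosed shortly before their EOS visit, a delay the protocol's own rule already implies. If every EOS visit came at least 90 days after the last dose, there is no delay.

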### **3.4. Unmasking**

#### **4. POPULATIONS DEFINITIONS**

The following analysis sets will be evaluated and used for presentation and analysis of the data.

Analysis sets defined by eye will be respect to each eye. For example, the Safety Analysis Set for the CE will be determined by measurements taken on the CE. The subject-level analysis sets consist of subjects who meet the criteria in at least one of the eye-level analysis sets.

**Screening Analysis Set:** Includes all subjects who signed the informed consent form.

**Safety Analysis Set (SAF):** All screened subjects who were randomized and received at least one dose of study treatment.

The disposition data will be presented for all screened subjects. The SAF will be the primary set for the analysis of the safety parameters. The SAF will also be used for descriptive summaries of demographics, baseline characteristics, and ocular/non-ocular medical history.

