### **5.4. General Statistical Methods**

All output will be incorporated into Rich Text Format (RTF) files and bookmarked PDFs, sorted and labeled according to the International Conference on Harmonisation (ICH) recommendations, and formatted to the appropriate page size(s).

Tabulations will be produced for appropriate disposition and demographic characteristics.

For measurements of continuous variables, summary statistics of absolute values will be reported and will include n, mean, standard deviation, median, and minimum and maximum values. The number of missing values will be displayed in parenthesis next to 'n'. Mean, standard deviation, median, will be presented with one more decimal place compared to the raw data, and minimum and maximum will be presented with the same number of decimal places as the raw data.

For categorical variables, summary tabulations of the number and percentage within each category of the parameter will be presented (as well as the number for missing data).

Denominator for percentages is column N. Percentages will be rounded to one decimal place.

Therefore, there may be cases where for instance the total of the percentages does not exactly equal 100%.

Where appropriate, data will be listed by eye (i.e., TE, CE).

In summary tables the study treatments will be presented in the following order: 'Ultevursen 180/60 µg', 'Ultevursen 60/60 µg', and 'All Subjects'.

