## **5.5. Study Population**

### **5.5.1. Subject Disposition**

Subject disposition, including the number of screened subjects, the number of subjects failed screening, the number of randomized subjects, the number of subjects who received study treatment in the TE, the number of subjects who received study treatment in the CE, who completed the study and the number of subjects who discontinued from the study, along with the reasons will be summarized by treatment group.

A listing of subject disposition will be generated, including the reason for premature study or treatment discontinuation, if applicable.

A listing of screen failure data will also be provided.

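### Does the SAP's wording about doses in the contralateral eye leave the ocular adverse event analysis undefined?

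*SAP*

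**What the plan says.** Protocol 4.2 is explicit about which eye is treated: "Dosing will be only in the TE (i.e., study eye). The CE will not be dosed". Protocol 10.3 agrees, since the TE is the eye treated after randomization. Protocol 4.2.1.3 has all ophthalmic assessments done on both eyes.

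SAP 5.6 tabulates ocular adverse events separately for the TE and the CE and gives a time origin for each: "Time to onset will be calculated in hours, relative to the last dose received in the eye experiencing the ocular AE". For non-ocular events the origin is the subject's last dose, "irrespective of which eye received the last dose (i.e., TE or CE").

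SAP 4 defines analysis sets by eye: "For example, the Safety Analysis Set for the CE will be determined by measurements taken on the CE". It then says: "The subject-level analysis sets consist of subjects who meet the criteria in at least one of the eye-level analysis sets". The Safety Analysis Set itself is: "All screened subjects who were randomized and received at least one dose of study treatment". SAP 5.4 adds: "Denominator for percentages is column N".

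The SAP provides for CE dosing in two further places. SAP 5.5.1 counts "the number of subjects who received study treatment in the CE", and SAP 5.7 includes a listing of study drug administration in the CE. SAP 6 states that the study was stopped early and that no formal statistical analysis will be produced.

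**The concern.** Read beside Protocol 4.2, the SAP appears to describe a study in which the second eye may be treated. Two consequences suggest themselves.

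- **Time to onset.** If the clock starts at the last dose in the affected eye and the CE never receives one, time to onset cannot be calculated for any CE ocular event. A programmer might leave it missing or choose another anchor.
- **Denominator.** If the eye-level Safety Set for the CE needs a dose in the CE, it is empty, and the CE adverse event percentages have a denominator of zero. If it needs only a treated subject with CE measurements, the denominator is every such subject. Two programmers could then produce different CE tables.

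Ocular adverse events are a secondary safety endpoint, and the eye-specific tables are among the few that the abbreviated SAP keeps. An ambiguous denominator there, or doubt about whether the CE is an undosed eye, would matter to a reader of the safety results.

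**Working it through.** **Inputs.** Planned size: 27 per group in three groups, about 81 in total (Protocol synopsis and 4.2). Administrations: Day 1, Month 3, then every 6 months, over 24 months (Protocol 4.2). CE doses planned: 0 (Protocol 4.2). Percentages over column N (SAP 5.4). The number actually enrolled is not given, so 27 and 81 are planned figures.

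**The plan's own figure.** 3 × 27 = 81, which agrees with the stated total.

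**Step 1: does a time origin exist?** Over a full 24 months the schedule gives the TE administrations at Months 0, 3, 9, 15 and 21, which is 5. The CE has 0. The SAP 5.6 ocular rule therefore works for TE events and returns nothing for events in an undosed CE. The non-ocular rule works throughout, because it does not depend on the eye. This part of the concern is confirmed.

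**Step 2: where would the missing value appear?** SAP 5.6 names overview tables of adverse events, summaries by system organ class and preferred term, and summaries of serious events and events of special interest. SAP 5.7 names by-subject listings. None is named as a time-to-onset output. The table shells are in a separate document that is not available here, so such a column cannot be excluded. If there is one, a CE event has no dose in its eye, and the natural entry is not applicable.

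**Step 3: is treatment-emergent status affected?** SAP 5.6 defines a treatment-emergent event relative to study treatment, sham included, and names no eye. SAP 5.6.1 imputes incomplete dates against the first administration date, again with no eye named. A CE event can therefore be flagged from the subject's first administration. The flag does not use time to onset.

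**Step 4: which CE denominator?** The two readings are:

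| Reading of the CE Safety Set | Planned N per group | 3 affected CEs (illustration) |
|---|---|---|
| Dose received in the CE | 0 | 3/0, undefined |
| Treated subject with CE measurements | up to 27 | 3/27 = 11.1% |

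The second reading follows from the text. The dose criterion speaks of subjects and names no eye. The sentence on the CE ties its set to measurements, and Protocol 4.2.1.3 has the CE measured as well as the TE. The first reading has to add a condition that is not written, and it would empty the two CE ocular tables named in SAP 5.6 and the CE baseline visual acuity summary in SAP 5.5.2. The subject-level Safety Set is the same under both readings, because every treated subject qualifies through the TE.

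**Step 5: what do the CE disposition count and listing show?** If no CE was dosed, the count is 0 and the listing is empty, and both are correct. If a CE was treated by mistake, they are where it would be recorded. Neither output needs CE dosing in order to be produced.

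**The case for a change.** The strongest opposing case is that the SAP says ocular time to onset will be calculated, so a programmer must do something for the CE, and the plan does not say what. The set definition refers to criteria at eye level without setting out how the measurement rule and the dose rule combine. One sentence would settle both points at almost no cost, and ocular safety by eye is central to what this close-out reports.

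A second argument concerns removed text. SAP 3.2 speaks of two periods of randomization but visibly describes one. If withheld text allowed CE dosing later, CE events before that dose, and events in CEs never dosed, would still have no origin. The two readings of the CE set could then give two different non-zero denominators.

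The first argument stands as a remark on drafting: the ocular rule was written without regard to an eye that is never dosed. It does not show that any planned result would come out wrong. Not applicable is an accurate entry, and the competing denominator would leave planned tables empty. The second argument is conditional on text that cannot be seen. The visible protocol allows changes to the treatment plan in general terms but provides for no CE dosing, and passages that are evidently incomplete are no basis for a finding. Even in that case, the measurement-based reading would still put treated subjects in the denominator, and the eye-specific time origin would make sense for the eyes that were dosed.

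**Conclusion.** The inconsistency exists, but no change to the plan follows from it. SAP 5.6 gives no time to onset for ocular events in an undosed CE, which under Protocol 4.2 means all CE ocular events. The effect stops there. CE event counts, treatment-emergent flags and the natural CE denominator (up to 27 per group as planned) are unaffected. The CE dosing count and listing are correct as zero and empty.

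Two features keep the matter small. Time to onset is not named as the content of any output in the SAP, and SAP 6 limits the work to descriptive tables and raw-data listings after early termination, so no test, estimate or comparison depends on it. Rewording would make the document tidier but would change no reported number.

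This rests on three assumptions: that no CE was dosed other than by error; that the unseen shells do not make CE time to onset a summary measure; and that programmers read the Safety Set as its wording suggests, by subject for dosing and by eye for measurement. The visible text supports the first and third. The second cannot be checked, but if it failed the consequence would be a column marked not applicable.

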10.9 Safety Analyses

10.9.1 Treatment Emergent Adverse Events

A treatment-emergent AE (TEAE) is defined as an event that was not present prior to administration of the first dose of study treatment and present after the first administration or if it represents the exacerbation of an event that was present prior to the first administration.

Adverse events noted during the study will be coded to system organ classes (SOCs) and preferred terms (PTs) using the Medical Dictionary for Regulatory Activities (MedDRA) dictionary. The overall incidence of TEAEs will be summarized by treatment group and classified by SOC and PT. Deaths, AE severity, serious AEs, relationship to study treatment and study discontinuation due to AE will also be tabulated by treatment group. An AE will be considered related to study treatment if the Investigator indicated the event is at least “possibly” related or if the relationship is missing. Adverse events with missing start dates, but with stop dates overlapping into the treatment period will be counted as treatment emergent. All AEs will be listed in subject listings and summarized by numbers and percentages of subjects by treatment group.

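### The SAP lists SOC/PT tables for ocular TEAEs only, so most non-ocular events are not tabulated by term and arm as the protocol promises; SAP 6 and the column order in SAP 5.4 also need correcting

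*SAP*

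**What the plan says.** Protocol 10.9.1 makes two commitments and limits neither to ocular events. The first concerns event terms: "The overall incidence of TEAEs will be summarized by treatment group and classified by SOC and PT". The second adds further breakdowns of the same events, again for each arm: "Deaths, AE severity, serious AEs, relationship to study treatment and study discontinuation due to AE will also be tabulated by treatment group".

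Protocol 4.1.2 names ocular and non-ocular AEs as the secondary safety endpoint.

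SAP 5.6 opens with "Adverse events will be summarized by treatment group separately as follows" and gives a by-subject counting rule for non-ocular events: "a subject contributes only once to the count for a given adverse event", at SOC or PT level. It then lists seven outputs: an overview for each eye, an overview for non-ocular events ("Overview of Non-Ocular Adverse Events during the overall study period (Safety Population"), SOC/PT tables of ocular TEAEs for the treated eye and the contralateral eye (the latter is "Summary of Ocular Treatment-Emergent Adverse Events for Contralateral Eye during the overall study period by MedDRA System Organ Class and Preferred Term"), SAEs, and AESIs. These are to be split into ocular and non-ocular where that applies.

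SAP 6 records that the sponsor stopped the study early and that there will be no formal analysis. It then says: "Only disposition, demographic and baseline characteristics, and overview of AEs will be summarized in tables".

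SAP 5.4 fixes the column order of summary tables as the two ultevursen regimens followed by all subjects. Sham is not named.

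**The concern.** The protocol promises a term-level comparison of all TEAEs between arms, and the SAP provides it only for the eyes. The SAP keeps a SOC/PT table for the contralateral eye, which Protocol 4.2 says is not dosed, but lists none for the rest of the body. It gives no reason for treating the two differently.

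With formal efficacy analysis gone, the AE tables are the main outcome summary left in the close-out report. An overview gives headline counts and does not show which event occurred in which arm. A non-serious systemic event that clustered on ultevursen would be merged into a total, and a reader would have to count it by hand from the listing.

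Two further passages add to the difficulty. Read literally, SAP 6 cancels the SOC/PT, SAE and AESI tables that SAP 5.6 lists. A programmer following SAP 5.4 literally would produce no control column to compare against.

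**Working it through.** The check is mainly a comparison of text. Each output promised in Protocol 10.9.1 was looked for in SAP 5.5.1 (disposition), 5.6 (AE tables), 5.7 (listings), 6 (changes) and 8 (shells).

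| Protocol 10.9.1 | Where it stands in the SAP |
|---|---|
| TEAEs by SOC/PT, ocular, treated eye | Listed in 5.6 |
| TEAEs by SOC/PT, ocular, contralateral eye | Listed in 5.6 |
| TEAEs by SOC/PT, non-ocular | Not listed; overview only |
| Serious AEs | Listed in 5.6 |
| Severity | No table named; may be an overview row |
| Relationship | No table named; may be an overview row |
| Deaths | No table named; may be an overview row |
| Study discontinuation due to AE | No AE table named; reasons for discontinuation by group are in the 5.5.1 disposition table |

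SAP 8 says that the shells are in a separate document, which was not available. The three rows marked as possible overview rows therefore cannot be settled either way. The missing non-ocular SOC/PT table can be settled, because SAP 5.6 names its SOC/PT tables one by one and both are ocular.

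**What remains for non-ocular events by arm.** There is the overview, the SAE and AESI tables where they include non-ocular events, and discontinuation reasons. SAP 5.7 adds a by-subject listing. What falls through is the group of TEAEs that are non-ocular, non-serious and not AESIs.

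**SAP 6 against SAP 5.6.** SAP 6 allows three kinds of table: disposition, demographics and baseline, and an AE overview. Of the seven outputs in SAP 5.6, three are overviews. The other four (two ocular SOC/PT tables, SAEs, AESIs) are outside what SAP 6 allows. Both statements cannot hold.

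**SAP 5.4 against SAP 3.1, 3.2 and 5.6.** Sections 3.1 and 3.2 define three randomised groups, and 5.6 promises AE summaries by treatment group. Section 5.4 names columns for two groups and a total. If the total includes sham, a reader could recover sham by subtraction (all subjects minus 180/60 minus 60/60), but the plan does not say so.

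**Illustration of what would not be seen.** This assumes the planned 27 per arm; the documents do not give the numbers actually randomised.

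- Ultevursen arms together: 27 + 27 = 54. Sham: 27. Total: 81.
- One non-ocular PT in 5 ultevursen and 0 sham subjects: 5/54 = 9.3% v 0/27 = 0%.
- Probability that five affected subjects all fall in the ultevursen arms by chance: (54 × 53 × 52 × 51 × 50) / (81 × 80 × 79 × 78 × 77) = 379,501,200 / 3,074,591,520 = 0.123, about 12%.

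Such a split would not be strong evidence of harm. It is the kind of pattern that a safety table by term exists to show, and here it would appear only inside a total unless the events were serious or AESIs.

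**The case against.** The strongest reply is that the reduction is declared. SAP 2.2 calls the plan abbreviated and directed at close-out and an abbreviated report, and SAP 6 gives early stopping as the reason. SAP 2.2 also begins as if text before it had been removed, so a fuller rationale may exist. This stands against any reading that the SAP dropped tables silently or without a reason. It does not account for the gap, however. Early stopping explains giving up formal inference, whereas a SOC/PT table is a descriptive count, and the SAP keeps two of them.

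A reader might infer that systemic safety can no longer be compared between arms. The documents do not support that: the non-ocular overview by treatment group, the SAE and AESI tables and the listing all remain.

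A reader might also infer that the severity, relationship, deaths and discontinuation summaries have been abandoned. That is not shown. They may be rows of the overviews, and reasons for discontinuation are in the disposition table, although the plan does not say that the event responsible will be identified.

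It is also tempting to say that the non-ocular counting rule has no table to serve. The rule covers any tabulation, so it can apply to the SAE and AESI tables.

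Finally, Protocol 2.5 describes the intravitreal route as minimising systemic absorption, which makes a systemic signal less likely. That lowers the stakes, but non-ocular AEs remain a named secondary endpoint.

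**Conclusion.** The point holds in a limited form. One protocol commitment is clearly unmet: non-ocular TEAEs by SOC and PT by treatment group. The loss is term-level tabulation of non-serious, non-AESI non-ocular events. SAP 6 contradicts SAP 5.6 on four of seven listed outputs, and SAP 5.4 leaves the sham column unstated. Four further items (severity, relationship, deaths, AE-related discontinuation) are unconfirmed and cannot be called missing.

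This rests on the SAP 5.6 list being complete and on the unseen shells not adding a non-ocular SOC/PT table. If they do, the remaining work is to align the SAP text with them. The 5/54 v 0/27 example shows only what would go untabulated; it is neither data nor a forecast, and actual arm sizes may be smaller after early stopping. The change should be made, but it is a reporting correction and does not affect the conduct of the study.

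**What to change.** 1. Add to SAP 5.6 one summary of non-ocular TEAEs by SOC and PT for the Safety Population, using the by-subject counting rule already stated there.
2. Correct SAP 5.4 so that summary tables show both ultevursen regimens, sham and all subjects.
3. Reword SAP 6 so that it names the AE tables in 5.6 instead of allowing only an overview, and state there any Protocol 10.9.1 summary that is deliberately not produced.
4. Check the shells. Confirm that the overviews give counts by arm for severity, relationship, deaths and AE-related study discontinuation, and add them as overview rows if they do not. Separate tables for each of these, split by eye and AE type, are not needed; the protocol does not ask for them.

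The cost is one more descriptive table, possibly a few overview rows, and edits to three SAP sections and the list of outputs. MedDRA coding (SAP 5.1), the counting rule and the parallel ocular tables are already planned, so the added programming should be small.
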